## 5. Research design

### 5.1 Overall design

In this single-arm, open-label, multicenter, prospective clinical trial, 50 cases of operable non-small-cell lung cancer requiring pneumonectomy were proposed to be enrolled. Patients will be treated with neoadjuvant or inductive combination therapy of immuno- and chemo- by evaluation from multidisciplinary discussion (Department of Thoracic Surgery, department of Respiratory Medicine, department of Radiology), than undergo open or minimally invasive radical surgery for lung cancer and systematic lymph node dissection. Peri-operative complications, lymph node dissection, R0 resection rate, and postoperative short-term and long-term efficacy outcomes will be recorded and evaluated.

Participating centers:

- 1 Ruijin Hospital, Shanghai Jiao Tong University School of Medicine, Shanghai, China
- 2 Shanghai General Hospital of Shanghai Jiao Tong University School of Medicine
- 3 The Ninth People's Hospital of Shanghai Jiao Tong University School of Medicine
- 4 Huadong Hospital, Fudan University Medical College, Shanghai, China

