### **5.3 Determination of sample size**

This study is a prospective observational clinical study, and the purpose of the study is to evaluate the feasibility and long-term outcome of pneumonectomy to lobectomy after neoadjuvant or induction chemoimmunotherapy for locally progressive non-small cell lung cancer. Due to the lack of previous reference data, the sample size was not calculated based on hypothesis testing, and 50 patients were enrolled.

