### **6.4 Methods of Study Subject Allocation**

This study is a single-arm clinical trial and does not involve the allocation of study subjects to the enrollment group.

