## **7.3 Measures to reduce bias: randomization and blinding**

This study was a single-arm study and did not involve randomization grouping and blinding.

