## 10. Statistical analysis

### 10.1 General methodology

All statistical analyses were performed using R software, and hypothesis tests were standardized using two-sided tests, giving the test statistic and its corresponding p-value.  $p<0.05$  was considered statistically significant, and 95% confidence intervals were set as required.

Statistical description: All indicators are described according to their nature. Qualitative indicators are expressed as frequencies and percentages of categories; metrics provide the number of cases, mean, standard deviation, median, minimum and maximum values.

Statistical inference: For overall survival time and disease-free survival time, overall survival curves and disease-free survival curves were plotted using the Kaplan-Meier method; risk differences between survival and disease-free survival were assessed using the Log-Rank test; multivariate analyses were performed using the Cox proportional risk model to assess the effect of subgrouping (surgical modality) and other prognostic factors on survival and disease-free survival. survival and disease-free survival. The t-test was used for measures that were normally distributed, and the rank-sum test was used for measures that were not normally distributed; the chi-square test was used for between-group comparisons of count data, and the Fisher exact probability method was used when necessary.

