### 10.2 Analysis of Primary and Secondary Study Endpoints

#### Primary Endpoints

Overall survival time (in months): Overall survival curves were plotted using the Kaplan-Meier method; the difference in survival risk between the two groups was assessed using the Log-Rank test with 95% confidence intervals; multivariate analyses were performed using the Cox proportional risk model to assess the effect of subgrouping (surgical procedure) and other prognostic factors on the survival risk, and 95% confidence intervals were given for each factor. A multivariate analysis using the Cox proportional risk model was performed to assess the effect of grouping factors (surgical modality) and other prognostic factors on survival risk with 95% confidence intervals for each factor.

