### 10.5 Subgroup analysis

For the primary study endpoints grouped by age, sex or other demographic,

clinicopathologic characteristics, and surgical treatment modalities, a Subgroup analysis was performed.

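### Section 10.2 makes overall survival primary and gives R0 by lobectomy, the declared primary endpoint of a single-arm trial, only a secondary test between two undefined groups

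*Protocol*

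**What the plan says.** On design, the protocol is consistent:

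- Section 5.1: "In this single-arm, open-label, multicenter, prospective clinical trial, 50 cases of operable non-small-cell lung cancer requiring pneumonectomy were proposed to be enrolled".
- Section 6.4: "This study is a single-arm clinical trial and does not involve the allocation of study subjects to the enrollment group".
- Section 7.3: "This study was a single-arm study and did not involve randomization grouping and blinding".
- Section 5.3: "Due to the lack of previous reference data, the sample size was not calculated based on hypothesis testing, and 50 patients were enrolled".

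On the primary endpoint, Section 5.2 names R0 resection rate (lobectomy) alone and lists OS among the secondary endpoints. Section 9.1 defines the primary endpoint as the share of patients whose tumour is completely removed by lobectomy, judged on pathology. The objectives in Sections 1.1 and 4 also rest on R0.

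On analysis, Section 10.1 sets a two-sided 5% level: "hypothesis tests were standardized using two-sided tests, giving the test statistic and its corresponding p-value". In Section 10.2 the primary heading holds one entry, OS, for which "the difference in survival risk between the two groups was assessed using the Log-Rank test with 95% confidence intervals". R0 comes under the secondary heading, with a chi-square test between two groups and nothing else. Section 10.5 separately lists surgical modality as a subgroup factor for the primary endpoints.

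**The concern.** Two parts of the protocol name different primary endpoints, and they cannot both be followed. An analyst working from Section 10.2 would report OS as the primary result. The question the trial exists to answer is how often patients facing pneumonectomy reach complete resection by lobectomy instead. That question would be left without a stated primary analysis. With two candidates on record, the choice between them could also be made after the data are seen.

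The method fits no better than the endpoint. A single cohort calls for an estimate, but Section 10.2 builds every endpoint around a contrast between two groups that the protocol does not define. A small p-value from such a contrast invites the reading that one operation is better than another.

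**Working it through.** There is no sample-size calculation to reproduce, because Section 5.3 says none was made. The check compares sections, counts entries and adds one interval.

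**1. Endpoint status, side by side**

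| Endpoint | Sections 5.2 and 9.1 | Section 10.2 |
|---|---|---|
| R0 by lobectomy | Primary; a proportion of patients | Secondary; R0 without the lobectomy qualifier; two-group chi-square |
| OS | Secondary | Primary; Kaplan-Meier, two-group log-rank, Cox |

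**2. Count of entries in Section 10.2**

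(1) OS; (2) disease-free survival (DFS); (3) surgical time, bleeding and transfusion; (4) intraoperative accidents; (5) lymph node dissection; (6) R0; (7) complications and mortality; (8) SF-36; (9) resting oxygen saturation; (10) lung function.

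A two-group test appears in 10 of 10. A multivariable model is given for OS and DFS only, so 10 − 2 = 8 entries have no adjusted comparison.

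**3. Which two groups?**

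The factor is called surgical procedure or surgical modality. Section 7.1.1 allows four resections (pneumonectomy, lobectomy, combined lobectomy, sleeve lobectomy), each open or minimally invasive. The background and the risk assessment suggest pneumonectomy against lobectomy or sleeve lobectomy. No section fixes the two levels, and the place of combined lobectomy is open.

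**4. Can the R0 chi-square answer the primary question?**

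Take the lobectomy-versus-pneumonectomy reading.

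- Under the Section 9.1 definition, success requires a lobectomy. The success rate in the pneumonectomy group is therefore 0 by definition, and the test says nothing about feasibility.
- Under the unqualified R0 of Section 10.2, the test compares clearance between operations. That is a different question from how often conversion succeeds.

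**5. What would the other contrasts mean?**

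On the same reading, the risk-minimising measures in Section 2.4.2 select patients who respond well and let frozen-section margins settle the operation. Group membership is then decided after enrolment by response and margins. An unadjusted difference mixes any effect of the operation with that selection. The Cox models for OS and DFS may reduce the mixing, but Section 10.2 does not name the other prognostic factors.

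**6. What a one-sample analysis gives at n = 50**

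Exact (Clopper-Pearson) 95% limits for x successes in n:

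- lower = Beta quantile 0.025 with parameters (x, n − x + 1)
- upper = Beta quantile 0.975 with parameters (x + 1, n − x)

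The protocol gives no expected rate, so x is assumed across a range:

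| x/50 | Rate | Exact 95% CI |
|---|---|---|
| 25 | 50% | 35.5% to 64.5% |
| 35 | 70% | 55.4% to 82.1% |
| 40 | 80% | 66.3% to 90.0% |
| 45 | 90% | 78.2% to 96.7% |

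For x = 40 the parameters are (40, 11) and (41, 10). The limits lie 13.7 points below and 10.0 points above the estimate. A usable primary analysis is therefore available with the planned 50 patients.

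**The case against.** The strongest defence is that comparing operations within one cohort is legitimate. Section 10.1 calls the factor a subgrouping. Section 10.5 plans subgroups by "clinicopathologic characteristics, and surgical treatment modalities, a Subgroup analysis was performed". Section 5.3 says only that the sample size did not come from a hypothesis test, which does not forbid testing. All of this stands. A reader might infer that a single-arm design rules out any comparison by procedure, and the documents do not support that. The fault is narrower: the levels are undefined, and the comparison displaces the one-sample estimate of the primary endpoint.

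A second defence is that Section 10.2 contains more than tests. It specifies Kaplan-Meier curves and Cox models for OS and DFS, quartiles and range for the operative measures, and confidence intervals for lung function. Section 10.1 adds that "Qualitative indicators are expressed as frequencies and percentages of categories", with 95% intervals where required. So it would be wrong to say that the ten entries are nothing but tests, or that no R0 percentage would ever appear. What is missing is any link between such a percentage, with its interval, and the primary endpoint.

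A third defence is that a separate statistical analysis plan, not at hand here, may settle the details. It may well settle the denominator. It cannot remove a contradiction in the protocol about which endpoint is primary.

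**Conclusion.** The point holds and should be corrected before analysis. Section 10.2 contradicts Sections 5.2 and 9.1 on the primary endpoint. It gives R0 only a two-group test that cannot answer the feasibility question, and it includes a contrast between undefined groups in all ten entries, eight of them without adjustment. These statements rest on the text alone. Step 5 and the definitional zero in step 4 assume a lobectomy-versus-pneumonectomy split, which the protocol suggests but does not state.

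Two further inferences are tempting and go too far:

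- A reader might put a figure on the false-positive rate caused by selection. That needs response rates, survival rates and selection strengths that the protocol does not give, and under weak selection the inflation could be small.
- A reader might say that the varying R0 phrases produce very different rates. Section 4 drops the lobectomy qualifier, but its sentence is still about conversion to lobectomy. A large numerical gap appears only if the reader supplies denominators that the protocol does not state.

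**What to change.** In Section 10.2:

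- List R0 by lobectomy as the primary endpoint and OS as secondary, in line with Section 5.2. Use the Section 9.1 definition wherever R0 is the primary measure.
- Analyse it as one proportion with an exact 95% confidence interval over a stated denominator, such as all enrolled patients.
- Report OS and DFS by Kaplan-Meier for the single cohort, timed from surgery as the 3-year rates in Section 9.1 are. Say how patients who are not resected are handled, since they have no such time origin.
- If comparisons by procedure are kept, define the two levels, including where combined and sleeve lobectomy fall, and label the comparisons exploratory and non-causal.

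The cost is protocol wording; no patients or data are added. The one loss is that between-procedure p-values can no longer be presented as confirmatory.

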### **8.3 Loss of Follow-Up**

Subjects will be followed up for a period of 3 years. Lost visits will be considered to occur when the subject stops scheduled follow-up visits, fails to complete the procedures specified in the study, or cannot be contacted by the investigator.

The investigator will follow the established follow-up plan, complete telephone and outpatient follow-up regularly, and communicate with the subject on a regular basis to minimize lost visits.

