#### Secondary endpoints

Disease-free survival time (in months): Disease-free survival curves were plotted using the Kaplan-Meier method; differences in the risk of disease-free survival between the two groups were assessed using the Log-Rank test with 95% confidence intervals; multivariate analyses were performed using the Cox proportional risk model to assess the effect of subgrouping factors (surgical procedure) and other prognostic factors on the risk of disease-free survival, with 95% confidence intervals for each factor. A multivariate analysis using the Cox proportional risk model was performed to assess the effect of grouping factors (surgical modality) and other prognostic factors on the risk of disease-free survival with 95% confidence intervals for each factor.

- Surgical evaluation indicators.
- Surgical time (unit: minutes), intraoperative bleeding (unit: ml), intraoperative blood transfusion (unit: ml): all quantitative data not conforming to normal distribution, calculate the median, 25% quartile, 75% quartile, the minimum value, the maximum value, and analyze the difference between the two groups by using the rank sum test.
- Incidence of intraoperative accidents: count data, using chi-square test to analyze the difference between the two groups.
- Lymph node dissection: the total number of lymph node dissection (unit: one) and the number of lymph node dissection at each station (unit: one) were non-normally distributed measurements, and the difference between the two groups was analyzed using the rank-sum test; the number of stations of lymph node dissection (intrapulmonary, hilar, and ipsilateral mediastinal lymph nodes) was count data, and the difference between the two groups was analyzed using the chi-square test. Differences between the two groups were analyzed using the chi-square test.
- Tumor R0 resection rate: count data, using the chi-square test to analyze the difference between the two groups.
- Perioperative, 30-day, and 90-day complication rates, and mortality rates: were count data, and differences between the two groups were analyzed using the chi-square test.
- Quality of Survival and Cardiorespiratory Function Evaluation at Admission, Discharge, 30 Days, and 90 Days
- Quality of Life Score SF-36 Scale: Percentage, as a non-normally distributed measure, use rank sum test to analyze the difference between the two groups.

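### Cox models for the 'effect' of the operation and an uncapped set of prognostic factors in 50 patients: possibly overfitted, imprecise in any case, and the operation's coefficient is not an effect

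*Protocol*

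**What the plan says.** The Protocol's section 10.2 describes the overall survival model thus: "multivariate analyses were performed using the Cox proportional risk model to assess the effect of subgrouping (surgical procedure) and other prognostic factors". For disease-free survival the purpose is "to assess the effect of subgrouping factors (surgical procedure) and other prognostic factors on the risk of disease-free survival". Both paragraphs ask for a 95% confidence interval for each factor. Section 10.1 repeats the plan, states that "hypothesis tests were standardized using two-sided tests", and sets the threshold at p<0.05. The other prognostic factors are neither counted nor limited, and no condition on the number of events is attached.

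On size, section 5.1 says that "50 cases of operable non-small-cell lung cancer requiring pneumonectomy were proposed to be enrolled", in a single arm. Section 5.3 says that "the sample size was not calculated based on hypothesis testing, and 50 patients were enrolled". On follow-up, section 8.3 says: "Subjects will be followed up for a period of 3 years".

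Two further places matter. Section 7.1.1 allows pneumonectomy, lobectomy, combined lobectomy and sleeve lobectomy. The risk-minimising measures in section 2.4.2 (assessment of potential risks/benefits) select patients who responded well to induction treatment and let intraoperative frozen pathology of the margins settle which operation is done.

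**The concern.** There are two separate problems.

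The first is information. What a Cox model can carry depends on the number of events, not of patients, and 50 patients over 3 years will yield few. With too many coefficients, hazard ratios become unstable and drift away from the null. With very few events, one surgical group may have none, and the ordinary estimate then does not exist.

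The second is meaning. The operation is decided after induction treatment and partly by what is found at surgery. Patients whose tumours responded less well are more likely to end with pneumonectomy and may also fare worse for that reason. Read as an effect of procedure, the coefficient would probably favour the smaller resection, which is what the Protocol itself expects. A publication could then present an imprecise and confounded hazard ratio as evidence about the operation. Section 10.2 places the overall survival model under its primary endpoints, although sections 5.2 and 9.1 name the R0 resection rate as primary. That is a separate inconsistency, but it makes it more likely that this model is given prominence.

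**Working it through.** The Protocol states no event number, power or expected survival for this population, so there is no figure of its own to reproduce.

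**Inputs from the Protocol:** N = 50 (5.1, 5.3); 3 years of follow-up (8.3); two-sided 0.05 (10.1).

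**Assumptions:** 3-year survival (S3) of 50-80%; 30% of patients in the smaller surgical group (a = 0.3); no dropout.

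**Anchor for S3.** The only long-term overall survival figure in the Protocol is 32% at 5 years, from a historical pneumonectomy series (2.2). With exponential survival, S3 = 0.32^(3/5) = 0.505, or 50 × (1 − 0.505) = 24.8 deaths. That series had neither this population nor this treatment, so it is used only as the pessimistic end of the range.

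**Formulas:**
- deaths d = 50 × (1 − S3)
- coefficients supported = d/10, rounded down
- SE of the operation's log hazard ratio = 1/√(d × a × (1 − a))
- 95% CI factor = exp(1.96 × SE)
- hazard ratio detectable with 80% power = exp((1.960 + 0.842) × SE)

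| Assumed S3 | Deaths | Coefficients at 10 events each | 95% CI: HR ×/÷ | Detectable HR, 80% power | Power for HR 2 |
|---|---|---|---|---|---|
| 80% | 10 | 1 | 3.87 | 6.9 | 17% |
| 70% | 15 | 1 | 3.02 | 4.9 | 23% |
| 60% | 20 | 2 | 2.60 | 3.9 | 30% |
| 50% | 25 | 2 | 2.35 | 3.4 | 36% |

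Over splits from 50:50 to 20:80, the CI factor runs from 3.45 to 4.71 at 10 deaths and from 2.19 to 2.66 at 25. Eighty per cent power for a hazard ratio of 2 needs (2.802/0.693)²/0.21 ≈ 78 events, more than the 50 patients.

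**Coefficients wanted.** The operation plus at least two other factors makes three, which needs 30 deaths, that is S3 = 40%. Entered as four separate procedures, the operation alone takes three.

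**Simulation** (n = 50, censoring at 3 years, 30% in the smaller group):
- *Spread.* With no true effect, going from 1 to 8 coefficients raised the SD of the operation's log hazard ratio from 0.71 to 1.08 at about 10 deaths, from 0.53 to 0.69 at about 20, and from 0.44 to 0.58 at about 25.
- *Drift from the null.* With a true hazard ratio of 2 (log 0.69), the mean log estimate moved from 0.71 to 0.88 at about 12 deaths and from 0.70 to 0.81 at about 24.
- *Fits that fail.* At about 10 deaths, roughly 5-10% of ordinary fits were not estimable, against none with Firth's method. In one set of runs the share was 4-6% whether the model had 1 or 8 coefficients, so a limit on covariates alone does not remove it. At 20 deaths or more it was nearly zero.

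**Disease-free survival.** Section 9.1 bases it on recurrence or metastasis. The Protocol gives no rate, so no event count is offered here.

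**The case against.** The best reply is that the choice and number of covariates commonly sit in a statistical analysis plan, which is not shown. That is right: the absence of a list is no fault in the Protocol. A model with one or two coefficients and 20 or more events would meet the usual rule of thumb. A reader might infer that these models are bound to be overfitted; the documents do not support this, because they do not fix the number of coefficients.

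A reader might also take a particular number of deaths as known. It is not. A range of 10-20 would already presume 3-year survival of 60-80%, and the Protocol's one historical figure points to about 25.

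Nor should the risk of spurious prognostic factors be put down to sparse events. With eight null covariates, simulation at 10-20 deaths gave at least one p<0.05 in about 33-40% of analyses. Eight independent tests give 1 − 0.95⁸ = 34% at any sample size. With three covariates one simulation gave 10-13%, against 1 − 0.95³ = 14%. This is ordinary multiplicity, and eight is itself an assumption.

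Finally, much of the imprecision comes from sample size, which no modelling rule can cure, and the planned confidence intervals would display it.

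What stands is what the Protocol itself has fixed: an ordinary Cox fit, open to any number of factors, tested at 0.05, with the operation's coefficient described as an effect. Confounding by response holds at any event count, and no covariate list drawn from baseline data would remove it.

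**Conclusion.** The point holds in a limited form. At an assumed 3-year survival of 50-80%, about 10-25 deaths support one or two coefficients at 10 events each. The survival models may therefore be overfitted unless the number of coefficients is limited, and near 10 deaths an ordinary fit may fail. The operation's hazard ratio will be imprecise even in the smallest model, with a 95% CI of about ×/÷ 2.4 to 3.9 under a 30:70 split. The same caution applies to disease-free survival, but its size cannot be stated.

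The firmest part needs no assumption about events: by the Protocol's own account, response and frozen margins help determine the operation, so its coefficient cannot be read as an effect of procedure. The ratio of 10 events per coefficient is a convention, not a threshold at which models become sound. These analyses belong to a feasibility study whose size was openly not based on a hypothesis test. The point therefore concerns how the models are specified and described, and does not by itself undermine the trial.

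**What to change.** In sections 10.1 and 10.2:

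- Replace the wording about an effect of surgical procedure by association, for both overall and disease-free survival.
- Report hazard ratios with 95% CI and make no significance claim.
- Group the procedures into one prespecified contrast, so that the operation takes one coefficient.
- Limit the number of coefficients by the observed events for each endpoint separately, for example about one per 10 events. This covers disease-free survival without a rate having to be assumed now.
- Fit with Firth's penalised likelihood.
- If events are too few, for example under 10, report Kaplan-Meier estimates only.

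The cost is wording; no patient, visit or data item changes. The downside is that fewer factors can be reported: at 10 deaths the procedure contrast alone uses the allowance and leaves no room for adjustment. The limit does not cure confounding by response, so the change to association is needed whatever the event count.
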